#### 1.9 PARTICIPANT SAFETY:

The safety of study participants will be monitored throughout the study. Study participants will undergo an extensive screening prior to entering the trial to determine that it is safe for them to participate in the intervention. Safety is continuously monitored during the intervention via two supervised sessions per week. We are aware of the potential for serious adverse events to occur with any type of exercise training. As such, the trial will take measures to reduce the risk of an adverse event. All individuals involved in human subject's research, regardless of whether exercise training is involved, are trained and certified in CPR and First Aid. We will have a medical monitor (cardiologist) who will review any exercise ECGs that are flagged for any unusual reading. Included in the exercise stress testing room is an automated external defibrillator (AED), should it be deemed necessary. Lastly, protocols are currently in place to respond to any adverse events that include contacting emergency response personnel and facilitating their arrival to the correct rooms.

The Data Safety Monitoring Board (DSMB), is responsible for monitoring study data for evidence of adverse effects attributed to the intervention. The DSMB also has the authority to recommend changes, stopping the trial at any time, or pausing the trial until problems are resolved. All AEs experienced by the participants during the study (Consent signing until end of study outcome collection) are to be reported during the regularly held DSMB meeting. The eBACH study will track the occurrence of:

- Serious Adverse Events (SAE)
- Unexpected Events
- Unfavorable medical events that occur during intervention sessions

The trial has created two forms for adverse event reporting. These documents have been created based on the belief that trainers and staff should not be responsible for determining whether the event is related to the intervention or whether/how it should be reported to the IRB and DSMB. Only the PI will determine if the event is (a) expected or unexpected, and (b) related to the intervention. Given the frequency of the interactions between subjects and trainers it will be important for trainers and staff to ask if the participant has had any illnesses, injuries, or medication changes since their last supervised exercise session. Based on responses to these questions, regardless of seriousness or relatedness, the trainer will complete a form documenting an adverse event. We have created a brief form for trainers (eBACH Adverse Event Form for

Trainers) for this purpose. Trainers or staff would first document the event on this form. This form allows trainers to circle the reported event (or provide an event not listed on the form). This completed document would be sent to the project coordinator who would then speak to the trainer and/or participant to find out more information about the event. The project coordinator would then complete the eBACH Event Evaluation Form based on this communication. This form has several sections with boxes available for documenting the reported severity (mild, moderate, severe), the chronicity (single occurrence, intermittent, persistent), whether the event was resolved or not, and whether it was related to the intervention and expected or unexpected. In particular, these forms are intended to clarify for the investigators, the IRB, and the DSMB, whether the adverse event was serious, whether the adverse event was related to the intervention, and whether it was expected or unexpected. An example of an expected adverse event from the exercise intervention would be muscle soreness which would be listed as a known risk in the IRB. An unexpected adverse event related to the intervention would be if someone falls off a treadmill and injures an ankle. The PI will oversee the determination of these events and if there is any question about whether the event was related to the intervention, its seriousness or expectedness, the event will be discussed at the weekly project meeting. For DSMB purposes, all adverse events that are reported will be recorded and separated based on whether the event was related to the intervention, unexpected, its seriousness, severity, chronicity, and resolution.

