#### 1.5.4 POST RANDOMIZATION TASKS:

Actigraph Link will be worn for one week every 6 weeks for each study participant. Measures of exercise self-efficacy are collected during the 3rd week of the intervention protocol.

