#### 1.8 INTERVENTION:

1.8.1 AEROBIC EXERCISE GROUP: Participants in the aerobic exercise condition will begin at a lighter intensity (50-60% Heart Rate Reserve or HRR) for 15-20 minutes during the first week of the program and gradually increase their intensity and duration by 5 minutes each subsequent week until they reach 60 minutes of exercise depending on the group (see more below). All exercise sessions start and end with 5-10 minutes of stretching for the purpose of warming up and cooling down. Levels of exercise intensity will be prescribed based upon maximal responses during the initial graded exercise treadmill test and then reassessed after the midpoint graded exercise treadmill test. As the participants will be low active at baseline, the prescribed intensity will be 50–60% of the maximum heart rate reserve for weeks one to six and 75–85% for the remainder of the program as long as it is deemed safe by the monitoring exercise physiologist and trainer. Participants that feel comfortable increasing their levels at a more rapid pace will be allowed to do so if the accompanying trainer also agrees that it is safe. Participants in the aerobic group will wear a heart rate monitor and be encouraged to exercise within their target heart rate zone. Heart rate intensity will be measured by a Polar H10 heart rate strap that is worn below their chest. Certified exercise instructors will closely monitor attendance, intensity, frequency, and safety. On-site exercise sessions will occur two days/week for the duration of the intervention and at home for one other day of the week. Compliance to home-based exercise will be monitored by exercise diaries.

**1.8.2 PHYSICAL ACTIVITY & HEALTH INFORMATION GROUP:** The control group will be asked to wear an ActiGraph daily monitor for 7 days every 6 weeks. They will not be given any information on exercise and they will not be asked to change their behavior or exercise patterns.

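### Adverse events and medication changes are solicited only at supervised exercise sessions; no equivalent query is specified for the control arm, so non-serious events will probably be under-recorded there

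*Combined protocol and SAP*

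**What the plan says.** Section 1.9 (Participant Safety) names the channel for safety monitoring: "Safety is continuously monitored during the intervention via two supervised sessions per week". It explains why trainers are used, "Given the frequency of the interactions between subjects and trainers", and says what trainers and staff should ask about: "illnesses, injuries, or medication changes since their last supervised exercise session". On the basis of the answers, "the trainer will complete a form documenting an adverse event", whatever the event's seriousness or relatedness. The project coordinator then follows up on a second form, and the PI decides expectedness and relatedness.

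For the exercise arm, section 1.8.1 says: "On-site exercise sessions will occur two days/week for the duration of the intervention". For the control arm, section 1.8.2 describes only a week of ActiGraph wear every 6 weeks. Section 1.5.4 gives the same wear schedule to everyone: "Actigraph Link will be worn for one week every 6 weeks for each study participant". Sections 1.5.5 and 1.5.6 repeat the baseline assessments at 6 and 12 months in both arms and list no adverse-event query.

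Section 1.9 makes the DSMB "responsible for monitoring study data for evidence of adverse effects attributed to the intervention" and requires that all adverse events from consent to the end of outcome collection be reported to it. The list of what the study will track is shorter: serious adverse events, unexpected events, and "Unfavorable medical events that occur during intervention sessions".

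**The concern.** A concurrent control arm shows how often illnesses, injuries and medication changes occur without the intervention. It can do so only if both arms are asked in the same way. Here the question itself refers to an event, the last supervised session, that a control participant never has. Exercisers are prompted about twice a week, while the plan states no prompt for controls. Mild events and new medications in controls would then reach the database mostly by chance or by spontaneous report.

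What is at stake is the DSMB's judgement, since it can recommend pausing or stopping the trial, and any by-arm adverse-event summary in the results. An apparent excess in the exercise arm could come from questioning alone, and a real excess could be dismissed on the same ground. For medication changes, unequal recording would also prevent a fair descriptive or sensitivity analysis of drugs started during the trial.

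**Working it through.** The documents give no adverse-event rate, no capture rate and no safety power figure, so there is no stated figure to reproduce.

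**1. Scheduled occasions for soliciting events over 12 months**

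| Occasion | Source | Exercise | Control | Event query stated? |
|---|---|---|---|---|
| Supervised sessions | 1.8.1 | 2 x 52 = 104 | 0 | Yes (1.9) |
| ActiGraph wear weeks | 1.5.4, 1.8.2, 1.8.3 | 52/6 = 8.7, about 9 | about 9 | No |
| 6- and 12-month assessments | 1.5.5, 1.5.6 | 2 | 2 | No |

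The 104 assumes full attendance. The figure of about 9 agrees with the count in section 1.8.3.

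**2. What unequal capture does**

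Let the true proportion of participants with any event be p in both arms, and let a share c_E of them be captured in the exercise arm and c_C in the control arm. Then the expected observed risk ratio = (p x c_E)/(p x c_C) = c_E/c_C, whatever p is.

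For illustration only, take 60 per arm (the amended target of 120, equally allocated) and c_E = 90%. Both capture rates and p are assumptions. The last two columns give the chance that a two-sided 5% test of two proportions would be significant, although there is no true difference.

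| c_C | Observed risk ratio | p = 30% | p = 50% |
|---|---|---|---|
| 90% | 0.90/0.90 = 1.00 | 5% | 5% |
| 70% | 0.90/0.70 = 1.29 | 12% | 20% |
| 50% | 0.90/0.50 = 1.80 | 36% | 64% |
| 30% | 0.90/0.30 = 3.00 | 73% | 96% |

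For example, with p = 30% and c_C = 50% the observed proportions are 0.30 x 0.90 = 27% and 0.30 x 0.50 = 15%. No such test is planned; the last two columns only show how misleading a by-arm table could look. Equal capture removes the distortion whatever the true event rate.

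**3. The tracked list against the rest of section 1.9**

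An event that is expected, non-serious and outside a session fits none of the three tracked categories. Yet the same section says that all adverse events are to be reported, and that the trainer's form is completed whatever the seriousness or relatedness. The list is narrower than the text around it.

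**The case against.** The strongest reply is that the comparison said to be distorted is not planned. Section 1.9 sorts events for the DSMB by relatedness, expectedness, seriousness, severity, chronicity and resolution, and arm is not on that list. Relatedness is judged case by case by the PI, and no by-arm table or test is specified. This stands: no prespecified analysis is affected. But the DSMB's task is to look for effects attributable to the intervention, and a by-arm summary is an ordinary use of such data.

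Second, controls are not wholly unquestioned. Staff as well as trainers may ask and document. The call before the blood draw (section 1.5.3, Session 3) asks about recent antibiotics, infection and cold symptoms, and would recur at 6 and 12 months in both arms. The Session 1 medication check may also recur. These soften the contrast but do not remove it: the first is a screen for rescheduling, the second is written as an eligibility step, and neither is stated as an adverse-event query. Two visits would not match about 104 sessions. The residency criterion mentions two visits a week, and section 1.6 mentions a first intervention session without naming an arm, but section 1.8.2 describes no sessions for controls.

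A reader might also draw three stronger conclusions that the documents do not support:

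- *Events during home exercise are missed.* The question covers everything since the last supervised session, so exercisers' home-session events are within its reach. Only the tracked list is too narrow.
- *Unrecorded medication in controls confounds systolic pressure reactivity and heart rate variability.* Medication started after randomisation is not a confounder of the intent-to-treat contrast, and no planned analysis uses medication change as a covariate or exclusion.
- *A particular inflation of the exercise-arm rate is established.* Any such figure depends on assumed capture rates.

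**Conclusion.** The point holds as a gap in what the trial collects. The only described routine for soliciting illnesses, injuries and medication changes is tied to sessions that one arm attends, and no query is specified for the other. If the plan is followed as written, non-serious events and medication changes will probably be under-recorded in controls, so that arm cannot serve as a fair background rate.

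The contact imbalance is firm on the stated schedules: about 104 occasions against none stated. The resulting bias cannot be computed. Under the illustrative assumptions an equal true risk would appear as a risk ratio of 1.29 to 3.00, which indicates direction and is not an estimate. Serious events are less likely to be missed, and the primary intent-to-treat estimates are untouched. The change should be made, but the trial's efficacy conclusions do not depend on it.

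**What to change.** 1. Ask both arms the same three questions (illness, injury, medication change) on the same schedule: at each 6-weekly ActiGraph wear period, about 9 a year, and at the 6- and 12-month visits. A short form or call accompanying the device would do.
2. Base any by-arm comparison of non-serious events and medication changes on these common responses.
3. Keep session-based questioning of exercisers unchanged. Continue to report serious events from every source, and send all session-elicited events to the DSMB in a separate listing. Restricting the DSMB to the common responses alone could hide real exercise harms, since recall over 6 weeks is incomplete.
4. Reconcile the tracked-event list in section 1.9 with the statements there that all adverse events are reported and that forms are completed whatever the seriousness or relatedness.

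The cost is a few minutes per wear period, protocol wording, and more control-arm events to process. The plan says only that the device is worn, so a brief staff contact may have to be added if none now exists.

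### The adverse event tabulation described for the DSMB does not list randomised arm, event enquiry is tied to sessions that only the exercise arm has, and no timing is given for serious events

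*Combined protocol and SAP*

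**What the plan says.** Everything on safety reporting stands in section 1.9 (Participant Safety).

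- **Duty and authority.** The DSMB "is responsible for monitoring study data for evidence of adverse effects attributed to the intervention". The next sentence reads: "The DSMB also has the authority to recommend changes, stopping the trial at any time, or pausing the trial until problems are resolved".
- **Route.** All adverse events from consent to the end of outcome collection "are to be reported during the regularly held DSMB meeting". No meeting interval is given.
- **Enquiry.** Trainers and staff ask about illnesses, injuries and medication changes since the participant's last supervised exercise session. They document what they hear, whatever its seriousness or cause.
- **Judgement.** "Only the PI will determine if the event is (a) expected or unexpected, and (b) related to the intervention". After a conversation with the trainer or the participant, however, "The project coordinator would then complete the eBACH Event Evaluation Form based on this communication". That form has boxes for relatedness and expectedness. The PI oversees the determinations, and doubtful cases go to the weekly project meeting.
- **Tabulation.** For the DSMB, "all adverse events that are reported will be recorded and separated based on whether the event was related to the intervention, unexpected, its seriousness", followed by severity, chronicity and resolution.

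**The concern.** The trial is randomised, so the strongest evidence on whether exercise causes harm is the difference in events between the arms. The tabulation described for the DSMB does not provide for that difference. Its only information on causation is the case-by-case relatedness judgement.

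Such a judgement works for events that point plainly to exercise, such as the two examples in section 1.9 (muscle soreness and a treadmill fall). It is weakest for events that also occur without exercise: illness, cardiac symptoms, or injury outside a session. Each of these may reasonably be called unrelated on its own, and an excess in one arm would then show only when the arms are set side by side with denominators.

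Two features add to this. The described enquiry reaches the arms unequally, so by-arm counts taken from it could mislead. And the section gives the DSMB a role in stopping or pausing at any time but does not say that a serious event reaches it before the next meeting.

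**Working it through.** The documents give no adverse event rate, harm boundary or DSMB operating characteristic, so there is no plan figure to reproduce. The check is mainly of text, with one piece of arithmetic on capture.

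**1. Is arm provided anywhere?** The sentence in section 1.9 has six separators: relatedness, expectedness, seriousness, severity, chronicity and resolution. Section 1.4 (Statistical Analysis) contains no safety analysis. Sections 1.10 and 1.11 cover missed visits and data quality, and the amendment text at the end covers sample size, accrual and recruitment. None gives event counts by arm, participants at risk or person-time.

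**2. Can relatedness stand in for arm?** The judgement is the PI's, and its information comes from the trainer or the participant. No blinding of the PI, coordinator or trainers is described. Relatedness to exercise can hardly be judged without knowing whether the person was assigned to exercise. It is therefore a judgement probably made with knowledge of the arm, and not an independent substitute for the comparison.

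**3. Would by-arm counts be comparable as events are now collected?**

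- Exercise arm (section 1.8.1): two supervised sessions a week for 12 months, 2 × 52 = 104 occasions for the enquiry.
- Control arm (section 1.8.2): one week of ActiGraph wear every 6 weeks, 52 / 6 = 8.7 a year (section 1.8.3 says about 9). No event enquiry is described at these.
- Both arms wear the ActiGraph on this schedule (section 1.5.4) and attend at 6 and 12 months (sections 1.5.5 and 1.5.6). These contacts are common to both arms.
- One of the three tracked categories in section 1.9, medical events during intervention sessions, can arise only where there are such sessions.

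Let both arms have the same true risk r, and let a control event be captured with probability c relative to an exercise-arm event. The apparent risk ratio is r / (r × c) = 1 / c. The documents do not give c, so a range is assumed:

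| Relative capture in controls (assumed) | Apparent ratio with no true difference |
|---|---|
| 0.70 | 1.4 |
| 0.50 | 2.0 |
| 0.30 | 3.3 |

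An arm column added to the present collection could therefore suggest harm where there is none.

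**4. When does a serious event reach the DSMB?** Section 1.9 names the regular meeting. It mentions that someone other than trainers and staff decides whether and how an event is reported to the IRB and the DSMB, but gives no timing. The authority concerns action at any time; the stated reporting route does not match that.

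**5. Who enters the judgements?** One sentence reserves expectedness and relatedness to the PI. A later one has the coordinator complete the form that carries those boxes, under PI oversight. Seriousness is not in the first sentence and appears only under the later oversight. The text does not settle whose entry is final.

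**The case against.** The best defence is that the six separators describe attributes recorded for each event and are not a report template. Arm is not excluded, and a DSMB charter or report shell outside these documents may provide it, along with prompt notification. This stands as a limit: the point is that arm and timing are not stated, not that they are ruled out. If a charter covers them, the protocol should cite it.

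A reader might also infer several stronger things that the documents do not support:

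- **That events judged unrelated are kept from the DSMB.** They are not. All adverse events go to it, and trainers document events whatever their cause. What is missing is the comparison, not the events.
- **That a serious event must wait for the next meeting.** The meeting is the only route stated, but the section does not call it the only one, and it leaves open how an event is reported. It also names the IRB as a recipient.
- **That the PI is stated to be unblinded.** This is inferred; no blinding status is given.
- **That there are two rival rules on who judges.** PI oversight, which extends to seriousness, softens the conflict to a tension in wording.
- **That the DSMB itself can stop the trial.** The sentence can be read as authority to recommend stopping.

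Finally, at the current target of 120 (60 per arm with equal allocation) by-arm event counts will be small. That is true, and such a table would inform the DSMB's judgement without serving as a formal test.

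**Conclusion.** The concern holds in this form. Followed as written, section 1.9 gives the DSMB a tabulation without the randomised comparison, without denominators and without stated timing for serious events. The event enquiry is also unequal by arm: about 104 supervised sessions a year against none, with about 9 ActiGraph weeks as the controls' regular contact between visits. The effect of unequal capture on an arm comparison, an apparent ratio of 1.4 to 3.3 with no true difference, rests wholly on the assumed capture of 70% to 30%.

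No size can be put on harm missed, because the documents contain no event rates and no meeting interval, and nothing here suggests that harm has occurred. The conclusion assumes that no charter outside these documents supplies the missing items. The change should be made because it is cheap and bears on participant safety; it does not affect the efficacy analysis.

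**What to change.** All changes are to section 1.9.

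1. **Tabulation.** In the closed DSMB report, show all events by randomised arm, with participants at risk and person-months per arm, whatever their attributed relatedness, and serious events first. Keep the six existing separators within arm.
2. **Equal enquiry.** Ask the same adverse event question on the same schedule in both arms, for example at the existing 6-weekly ActiGraph contacts and the 6- and 12-month visits. Base the by-arm table on those answers plus serious events. Report events elicited at supervised sessions separately.
3. **Timing.** State that serious events, and unexpected events judged related, go to the DSMB once that determination is made. Keep the regular meeting for the cumulative table.
4. **Responsibility.** Reconcile the two sentences on the PI and the coordinator, and say who enters relatedness, expectedness and seriousness.

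The cost is a short question at contacts that already exist, a notification per serious event, one grouping variable with denominators and a form instruction. The by-arm counts will be small and should be labelled as support for DSMB judgement, not as a test. No endpoint or eligibility criterion changes.
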